Some private identifiable information about individuals will be collected to enroll and contact participants. This information will be collected primarily via paper forms, which will be stored in locked filing cabinets at the research facility and only be accessible by study staff and other authorized individuals (e.g., members of the University of Florida Institutional Review Board). This includes a master list connecting participant study identification numbers to participant names.

Research data will be entered and stored on a secure server at the University of Florida, with no identifying information. Lab data (including monitor readings, breathalyzer readings, and information related to drinking such as timing and number of beer) and field data (including monitor readings and self-reports using EMA) will be linked using study ID. None of the study documents or communications with participants will directly identify the study as related to HIV. HIV status will be coded with the code key stored separately in a protected file on UF server. The code key will be destroyed after the study conclusion. No results will be published in a personally identifiable manner.

All NIH-funded studies collecting sensitive data are now considered to be granted a Certificate of confidentiality.

This certificate will protect the confidentiality of all research records generated by this study. Individually identifiable health information will be protected in accordance with the Health Insurance Portability and Accountability Act of 1996. All research personnel will be trained on human subjects' protection and HIPAA procedures.

Florida law requires reporting of newly discovered HIV cases. If participants test positive for HIV, we will do the following:

- Refer each participant to the Alachua county Health Department for another confirmatory test.
- Provide information on medical and support services available to the participant; and
- Discuss information on the importance of notifying previous and current sexual partners that they may have been exposed to HIV and how to prevent HIV transmission.

2. Alcohol consumption: Participants will only be enrolled in the study if they self-report consuming the requisite level of alcohol use. This minimum level of alcohol consumption greatly decreases the likelihood that any individual in this study will consume alcohol at a level greater than to which they are accustomed. Participants will also be excluded should they self-report any condition that contraindicates alcohol consumption (e.g., a history of clinically significant withdrawal detected at the in-person screening). Females will be screened for pregnancy at the in-person screening, as well as during the pre-session appointment on the day of the alcohol drinking session. Also, considering the health consequences of alcohol use on persons living with HIV, we only administered 3 beers to remain below the binge drinking limit.

Alcohol drinking sessions will be conducted by research staff who are experienced with these methods and have been carefully trained. As described above, all participants will be under supervision to prevent possible accidents. Several steps will be taken to ensure that alcohol consumption in this study occurs in a safe manner, in accordance with the

recommended guidelines on ethyl alcohol administration in human experimentation, set forth by the National Advisory Council on Alcohol Abuse and Alcoholism (2005).

Participants will not be permitted to drive themselves to alcohol drinking sessions, which will decrease the likelihood that individuals will attempt to drive after consuming alcohol as part of this study. Participants will not leave the laboratory facility on the University of Florida campus where the study will be taking place during the self-administration procedure. Given that smoking is not allowed on the University of Florida campus, this necessitates exclusion of individuals who are currently nicotine dependent as we will not be able to allow them smoking breaks during the alcohol drinking period and nicotine deprivation may present a confound to the results of this study. Participants will be asked to remain at the research facility until their breath alcohol concentration drops to the safe level of 0.00%. When it is time for dismissal, participants will be provided transportation (either university shuttle, Uber, or Taxi service) directly home by the study.

Several protocol features diminish the chance that study participants will leave the bar lab before dismissal by study staff and we have plans in place in case this occurs. As part of the informed consent process, we advise all participants of study requirements, including the requirement to stay until their BrAC falls to a safe level. We reiterate these requirements verbally before the alcohol drinking session. Thus, participants are made aware multiple times of the requirement to remain in the facility for at least two hours after the end of the alcohol drinking period and until they reach a safe BrAC. The pay structure of the study also discourages early departure. We pay participants \$15/hour for the alcohol drinking session, so participants will receive only a prorated portion of the payment should they end the session early.

Administration of alcohol to individuals in treatment for addictive behaviors could potentially impede the progress of their recovery. As a result, we will not enroll individuals who have taken part in inpatient or intensive outpatient treatment for alcohol use or other addictive behaviors in the past 12 months. Further, we will not enroll individuals with a lifetime history of clinically significant withdrawal from alcohol; a lifetime history of medical intervention for withdrawal or who currently present in a manner suggestive of withdrawal, based on the Clinical Institute Withdrawal Assessment for Alcohol (CIWA-Ar). These steps regarding withdrawal will also have the benefit of excluding individuals who are severely dependent on alcohol, for whom alcohol consumption in this study may not be safe.

3. Breath screening, urine tests and HIV oral swabs testing: All these noninvasive tests were performed as safeguards or for confirming eligibility, so there is minimal risk. If participants become emotionally distressed by the test results (e.g. unexpected positive result for pregnancy or HIV), our staff will receive basic training to help calm them down but will refer them to a clinical psychologist at UF (e.g., [name] who is also part of the SHARC team) if necessary. Persons become newly aware of their HIV+ status will also be referred for care linkage at the Department of Health or UF Infectious Disease department.

4. Questionnaires and interview: The major risk of the assessments is potential loss of confidentiality, which we have addressed above. To minimize any discomfort associated with reporting sensitive behaviors, participants will be informed that they may refuse to respond to questions that they are not comfortable answering. Questions related to eligibility determination and monitoring of safety and treatment response are not optional. If a person

declines to answer these questions, we will advise them that they will not be able to participate.

5. *Alcohol monitoring using wrist and ankle monitors:* The risk for breach of confidentiality associated with these monitors is very low. The data will be stored in the monitor's data porter and will be downloaded to secure UF drives after each lab session and the field test. Only study ID will be used to link the data.

6. *Ecological momentary assessment (EMA) of self-reported drinking:* The risk for breach of confidentiality associated with the EMA app is very low because of its encrypted cloud-based storage (described above). Additionally, the App will need the study ID to collect data, with no requirement of other personal information (e.g., phone number). To encourage participants to take time every day to complete the assessment, they will receive a bonus (\$70 additional to the base payment of \$70) for completing at least 80% of the EMA assessments.

8. Possible Benefits:

There are no direct benefits to participants, although some persons enjoy participating in studies that can provide information to help others.

9. Conflict of Interest:

N/A

References

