This study will include two parts: laboratory and field validation of the Skyn monitor (Fig. 2). We will need complete data from 20 HIV+ drinkers (~50% male) and 20 HIV- drinkers (~50% male), but we will screen to 160 participants to account for potential screen failure and drop out. Participants will be invited to complete all components of the study or only the field test portion given the COVID pandemic. The PI will decide who will complete all components and who will complete only the field testing. Participants will first complete an alcohol administration session (Lab Session 1) at the simulated bar lab, where they will consume 3 standard drinks (i.e., 3 12oz beers) at a determined consumption rate (30min). The transdermal alcohol concentration (TAC) readings collected from the Skyn monitor will be compared with breath alcohol concentration (BrAC) and may be compared with the Secure Continuous Remote Alcohol Monitor (SCRAM; Alcohol Monitoring Systems, Inc.) anklet. After completing Lab Session 1, during a two-week field test, participants will use the Skyn monitor and record drinking episodes using an EMA app. After the field test, participants will return to the bar lab to complete a second alcohol administration session using the same procedures as in Lab Session 1 to obtain test-retest reliability of the monitor. They will also complete a questionnaire on the acceptability and usability based on their experience with the Skyn monitor and its smartphone app.

Of note, BACtrack Skyn monitor has been approved in our previous study ([IRB201700455](#) for laboratory alcohol administration study where participants wear the monitor while they self-administer alcohol in the bar lab).

[figure not shown]

Figure 2. Study Procedures

Participants

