We will encourage each HIV+ drinker to refer up to 3 other drinkers, including persons that they suspect are HIV-, to participate. This will provide a comparison sample of HIV- drinkers who are likely to be of similar age and socio-economic status as the HIV+ participants. Additional inclusion criteria include self-reported ≥5 days with at least 1 alcoholic drink, and ≥1 days with at least 3 drinks (the level of alcohol consumption in lab sessions) in the past 30 days. Exclusion criteria include recent addiction treatment or treatment seeking; urine positive for illegal drugs except THC (not applicable to those who are only invited to do field test); past & current alcohol withdrawal; severe alcohol use disorder (DSM-5); meeting criteria for current nicotine dependence (not applicable to field only participants) or current substance use disorder (excluding mild cannabis use disorder and mild/moderate alcohol use disorder); medical conditions (other than HIV) contraindicating alcohol; pregnancy/breastfeeding in women; psychosis or other severe psychiatric conditions. Current use of antidepressant medication will not be an exclusion criteria for participants who are only completing the field test portion of the study.

Screening

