Potential participants will be contacted via phone call using their contact information in the Florida Cohort Registry, or they will contact our research staff if they are referred by others (i.e., HealthStreet, already enrolled participants) or self-referred (i.e., see our flyers in local HIV clinics). A trained research assistant (RA) will introduce the study and ask a few screening questions if the participant expresses interest. If the participant meets preliminary eligibility, the RA will schedule an in-person screen. For those who are asked to complete the field test only, portions of the in-person screening can be done remotely via phone call or password-protected UF zoom . If participants do not meet the preliminary eligibility, their data will be destroyed once their study status becomes clear. The in-person screen will include informed consent (can be signed in-person or as eICF through REDCap which will be sent via email), breath alcohol test (not applicable to field only participants), HIV test (only conducted on persons of unknown status to confirm HIV- status for the comparison group), drug and pregnancy test (women) (not applicable to field only participants), vital sign, height and weight collection, timeline followback (TLFB)⁴⁹ for past 30-day alcohol use, and diagnostic interview for substance use disorder/withdrawal. The measures used at this step include the “Clinical interview measures” and “Timeline followback”. The CIWA (which is included in the “clinical interview measures”) may be waived for HIV+ participants who complete the screening remotely. The SCID-V will also be conducted at this time, to assess

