for current and past substance use disorders. The screen will take approximately 2 hours, and participants will receive \$20 for completing it. Participants who come to their in-person screen as originally scheduled will be provided an additional \$10 payment. If screening is done remotely participants will receive \$10 as compensation for using their phone minutes and \$10 for completing the first set of questionnaires. They will receive \$10 for coming in to pick up the skyn device and completing the second half of the in-person screen plus an extra \$10 if they keep their originally scheduled appointment. HIV+ participants who complete the entire screening remotely will have the option of having the skyn device and other study materials mailed to them to their preferred address. For participants who are HIV+, we will ask them to bring in medical records of their most recent HIV lab values (CD4/Viral load) at any in-person appointment and will provide \$20 compensation for doing so. If the participant shows up for the in-person screening but the appointment needs to be rescheduled due to reasons on our end (e.g., logistic issues), then they will still receive the \$20 for this appointment. Those eligible will be scheduled for two drinking sessions. For those who screen out at the in-person screen, their data collected up to the point will be retained in the same way as those who are deemed eligible, because they sign the consent form before going through the in-person screen. However, like other participants they have the right to revoke authorization to use their data in writing. Screening documents will be assessed by [name] to confirm eligibility, a signature will be provided only if the participant is eligible.

Participants will be given the option to receive an e-gift card, or receive the gift card via mail, if they do not want travel to UF campus to pick up a gift card.

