Analysis plan for Aim 2. *Validate Skyn monitor in daily life using a 2-week ecological momentary assessment (EMA), and evaluate its acceptability and usability for daily use.* H2a. Agreement between monitor and self-reports in EMA. Using the same definition of a successful detection and procedure of determining drinking episode in monitor data as in

H1a, we will calculate the detection rates by self-reported number of drinks. A receiver operating characteristic (ROC) curve will be plotted. H2b: Relationship between TAC and number of drinks. First, simple correlations will be calculated to examine the association between TAC (peak, AUC) and self-reported number of drinks using all drinking episodes. Second, a multilevel analysis will be used to examine the association between TAC (peak, and AUC) and number of drinks accounting for nested data within person. Acceptability and Usability. Ratings of the Skyn monitor will be summarized on aspects such as wearability, ease to operate, satisfaction with the product, and willingness to wear.

Analysis plan for Exploratory Aim. *Explore factors that may be associated with individual differences in monitor readings.* T-tests or Chi-square will be used to examine group differences (e.g., male vs. female, HIV+ vs. HIV-) in TAC parameters (i.e., peak, time-to-peak) and their relationships with # of drinks and BrAC.

Sample size and power. This is for how many participants need to complete the study. For Aim 1, the sample size was based on prior laboratory validation studies of transdermal alcohol monitors.^{36,45,57} Also, power analysis shows that a sample size of 40 will give us 80% power to detect a correlation $\geq .60$. For Aim 2, power analysis shows that $n = 40$ will give us 90% power ($\alpha = .05$) to detect an effect size $\geq .13$ in a multilevel analysis with $r = .60$ between measures.^{58,59} For Exploratory Aim, $n = 20$ in each group can give us 80% power to detect a large difference ($d \geq .80$).

7. Possible Discomforts and Risks:

Potential risks in this study include:

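### Exploratory HIV+ versus HIV- comparisons of field data may be confounded with study pathway, and the planned tests make no allowance for it

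*Combined protocol and SAP*

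**What the plan says.** All references are to the combined protocol and SAP.

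- **Two pathways.** Section 6, Overview: "Participants will be invited to complete all components of the study or only the field test portion given the COVID pandemic". The allocation rule follows: "The PI will decide who will complete all components and who will complete only the field testing". No criterion, balancing by HIV status or recording of reasons is described.
- **Remote screening.** Section 6, Screening, opens partial remote screening to field-only participants whatever their HIV status: "portions of the in-person screening can be done remotely via phone call or password-protected UF zoom". The fully remote route is written for one group only: "HIV+ participants who complete the entire screening remotely will have the option of having the skyn device and other study materials mailed". The withdrawal assessment (CIWA) also "may be waived for HIV+ participants who complete the screening remotely".
- **Entry criteria.** Section 6, Participants, lists exclusions that depend on pathway, for example "meeting criteria for current nicotine dependence (not applicable to field only participants". The urine drug result, the distance limit and antidepressant use are also treated more leniently for field-only participants.
- **Preparation.** Hands-on practice with the apps and monitor is described under Lab Session 1. Under Field Test, field-only participants receive instruction when they collect the device.
- **Analysis.** Section 6, Analysis plan for Exploratory Aim: "T-tests or Chi-square will be used to examine group differences (e.g., male vs. female, HIV+ vs. HIV-) in TAC parameters", and in how those parameters relate to drinks and to breath alcohol (BrAC). Adjustment, stratification or restriction by pathway is not mentioned there or elsewhere.

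**The concern.** The HIV- drinkers are in the study to serve as the comparison group. The Screening text also says that findings on person-to-person variation in TAC and on field compliance are meant to feed a larger project.

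The two pathways can differ in who enters (smoking, drug-test result, antidepressant use, distance) and in how people were introduced to the device. If the mix of pathways differs between HIV groups and pathway affects field readings, an unadjusted comparison puts the pathway difference into the HIV difference. Nothing in the plan keeps the mix similar, reports it or allows for it. At stake is a false lead about monitor performance in HIV+ drinkers, or a real difference masked, depending on the direction of the pathway effect.

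**Working it through.** **Inputs from the documents.** 20 HIV+ and 20 HIV- completers (section 6, Overview). 80% power for d of at least .80 in the Exploratory Aim (section 6, Sample size and power). Alpha and sidedness are not stated for this aim.

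**Inputs assumed.** Field-only share by HIV group, and pathway effect D on a field outcome of 0.3 to 0.8 SD. One summary value per person, 20 per group, 5% level.

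**Step 1: the plan's own figure.** For two means with 20 per group and d = 0.80, power by the noncentral t is 79.9% one-sided and 69.3% two-sided. The stated 80% is reproduced only by a one-sided test. Two-sided figures are used below.

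**Step 2: bias of the unadjusted contrast.** Bias = D × (field-only share in HIV+ minus share in HIV-).

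- 20 points: 0.3 × 0.2 = 0.06 SD; 0.8 × 0.2 = 0.16 SD
- 40 points: 0.3 × 0.4 = 0.12 SD; 0.8 × 0.4 = 0.32 SD
- 60 points: 0.3 × 0.6 = 0.18 SD; 0.8 × 0.6 = 0.48 SD

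**Step 3: effect on the t-test.** Simulated rejection rates at two-sided 5% with no true HIV difference (20,000 runs per cell), for D from 0.3 to 0.8 SD:

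| Field-only, HIV+ vs HIV- | Bias (SD) | False rejection |
|---|---|---|
| 10/20 vs 10/20 | 0 | 3.5% to 4.9% |
| 12/20 vs 8/20 | 0.06 to 0.16 | 5.2% to 5.6% |
| 14/20 vs 6/20 | 0.12 to 0.32 | 6.5% to 13.6% |
| 16/20 vs 4/20 | 0.18 to 0.48 | 8.5% to 28.0% |

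The distortion is negligible at a small imbalance and serious at a large one.

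**Step 4: cost of adjustment.** With equal groups, phi = (p1 - p0) / (2 × sqrt(p(1 - p))), where p is the overall field-only share. The variance inflation is 1/(1 - phi²).

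- 60% vs 40%: phi = 0.2/(2 × 0.5) = 0.20; inflation 1.04; standard error 2% wider.
- 60% vs 20%: phi = 0.4/(2 × sqrt(0.24)) = 0.408; inflation 1.20; standard error 10% wider (sqrt(1.20) = 1.095).
- 80% vs 20%: phi = 0.6/(2 × 0.5) = 0.60; inflation 1.56; standard error 25% wider.

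Two-sided power for d = 0.80 falls from 69.3% to 67.5% at 12 vs 8, 61.7% at 14 vs 6 and 50.4% at 16 vs 4.

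**Step 5: cost of restriction.** If the fully remote HIV+ participants are left out, two-sided power for d = 0.80 is 66.9% with 18 vs 20 remaining, 62.3% with 15 vs 20 and 51.4% with 10 vs 20. If only all-component participants are kept, it is 56.2% with 15 per group and 39.5% with 10 per group. These counts are illustrations; the documents give none.

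**Step 6: what a covariate cannot do.** By the text, no HIV- participant is in the fully remote, mailed-device cell. A two-level pathway indicator gives that cell the same effect as other field-only participation. Any effect of its own stays mixed with HIV status, so only leaving those participants out deals with it.

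**The case against.** A reader might infer that HIV+ participants will be over-represented among field-only participants, so that HIV status is confounded with pathway. The documents do not show this. The field-only option is tied to the pandemic, not to HIV. Discretion alone creates no association with HIV status. Partial remote screening is open to all field-only participants, and so is returning the device by post. The HIV+ wording of the fully remote route also has a plain reason available in the text: people of unknown status need an HIV test to confirm that they are HIV-, and section 7 (Protection against Risks) places that testing at the research offices. This objection stands, and the concern is therefore one of possibility.

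A reader might also extend the point to the whole exploratory comparison. That does not hold either. BrAC exists only for laboratory sessions, and time-to-peak is analysed only under Aim 1. Everyone in those data is an all-component participant, so pathway cannot vary. What remains is peak TAC and its relation to number of drinks where these come from the field, and the plan does not say which data source it will use.

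Two of the suggested mechanisms are weaker than they look. Current substance use disorder, apart from the milder forms the plan allows, still excludes field-only participants; only the urine result is waived. The documents do not say that field-only participants go untrained. Baseline data are to be used to explore variation in TAC, but no adjusted HIV comparison is specified.

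Finally, adjustment has a price, and it is highest where the imbalance is greatest. That is right, and step 4 shows it. It argues for labelling the restricted analyses as sensitivity analyses, not for leaving pathway out.

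**Conclusion.** The concern holds in limited form. Any HIV comparison based on field data is open to pathway bias, and the plan has no step that would detect or reduce it. The size cannot be derived from the documents. Under assumed pathway effects of 0.3 to 0.8 SD, the bias is 0.06 to 0.16 SD at a 20-point difference in field-only share and 0.18 to 0.48 SD at 60 points, against the plan's detectable d of .80. With equal shares there is no bias.

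The comparison is exploratory. Aims 1 and 2 are not HIV contrasts, and laboratory TAC and BrAC comparisons contain a single pathway, so neither is directly affected. The change is worth making because it uses information the study already holds, but confidence that the bias is large is low.

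**What to change.** 1. Tabulate pathway (all components or field only) and screening mode (in person, partly remote, fully remote with mailed device) by HIV status, and state the considerations that governed pathway assignment.
2. For field-derived outcomes, replace the t-test with a linear model, or a multilevel model where episodes are the unit, containing HIV status and a pathway indicator. Where the question is how TAC relates to number of drinks, let that slope vary by both HIV status and pathway.
3. Repeat the comparison (a) in all-component participants only and (b) after excluding fully remote, mailed-device participants. Label both as sensitivity analyses.
4. State for each exploratory comparison whether it uses laboratory or field data.

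**Cost.** A change to the analysis text, with no new data. The main model loses one degree of freedom for pathway, or two if the slope term is added. Its standard error for the HIV contrast is about 10% wider at 60% versus 20% field-only and about 25% wider at 80% versus 20%. The restricted analyses lose further precision and should be read for direction and consistency, not significance.
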